1 INTRODUCTION

The statistical analysis plan proposed below details the necessary aspects to know about the study and the statistical methods to be used to apply them in the final statistical analysis.

2 STUDY RATIONALE

Surgical resection is the optimal first-line treatment for primary and metastatic liver cancer. However, few patients are suitable for surgery due to poor baseline function, overall tumor burden, or hepatic vessel invasion. In addition, surgery is an invasive method associated with a high morbidity. Chemotherapy and radiotherapy treatments are often ineffective treatment strategies for liver cancer treatment, outweighed by frequent toxicity or collateral damage.

Ablation techniques have emerged as promising alternatives for those patients who are not eligible for surgical resection or who have failed medical and/or radiotherapy therapies. However, despite the efficacy of some of these local thermal ablation modalities, significant limitations exist due to their mode of action (thermal tissue destruction), including the heat sink effects from blood flow through the highly vascular liver, often resulting in incomplete tumor ablation or inability to treat near major blood vessels. In addition, uncontrolled thermal spread (ablating beyond planned volumes) increases the potential for damage to adjacent structures. Therefore, developing new strategies in which a liver tumor can be ablated non-invasively and avoiding thermal-related collateral damage and ineffectiveness would be a major clinical advancement in the treatment of soft tissues, particularly liver tumors.

To address these unmet clinical needs, cavitation-based focused ultrasound (histotripsy) is a promising option to ablate liver tumors and overcome the limitations of currently available ablation modalities. Histotripsy is a non-invasive, non-thermal, image-guided focused ultrasound ablative technology that uses mechanical properties of focused ultrasound to ablate targeted tissues through the precise delivery of acoustic cavitation. Histotripsy has the potential to target multiple sites without the need for incisions or needle insertions (which may cause bleeding, infection, and/or tumor spread). Because histotripsy is non-thermal, it is not affected by the heat sink effect from blood vessels and does not have the limitations associated with thermal ablation such as collateral damage due to uncontrolled thermal spread. In addition, histotripsy may be able to overcome the interference challenge from overlying ribs better than other ablation methods. It has been demonstrated preclinically that histotripsy can generate liver ablations using acoustic energy transmitted through the ribcage without inducing unwanted thermal effects or damage to overlying tissues. Liver ablation using histotripsy results in complete ablation of target tissue into an acellular homogenate that is absorbed by the body and replaced by normal liver parenchyma over time.

As has been demonstrated through extensive preclinical experience, histotripsy is a potential paradigm-shifting technology. The non-thermal and non-invasive characteristics of histotripsy offer patients the potential for a soft tissue/tumor ablation with fewer clinical complications and adverse events than currently available ablation methods and surgical procedures.

The safety of the VORTX Rx® has been demonstrated through rigorous performance testing to include bench and preclinical acute and chronic studies. This clinical study is intended to evaluate technical performance, including acute technical success, while collecting safety-related data of ablation using the VORTX Rx®.

3 OBJECTIVES AND DESIGN

3.1 Study objectives

Primary objective

The primary objective of the study is to evaluate the acute technical performance of the VORTX Rx® medical device for the ablation of primary and metastatic liver tumors.

Secondary objectives

1. Assessment of the safety profile of the VORTX Rx®.
2. Assessment of local tumor progression by MRI at 1 week, 1 month and 2 months, post-procedure.
3. Assessment of the involution of the ablation zone 1 week, 1 month and 2 months post-procedure.
4. Assessment of liver panel.
5. Immunologic assessment.
6. Evaluation of quality of life.
7. Assessment of pain and analgesic requirements after the ablation procedure.

3.2 Study population

This study will include up to ten (10) subjects meeting all the inclusion criteria and none of the exclusion criteria, and giving their informed consent to participate in the study.

Inclusion criteria

1. Written informed consent before any study procedure is performed.
2. Subjects of both sexes aged 18 years or older.
3. Patients diagnosed with liver cancer, including HCC or liver metastases from breast, lung, pancreas and/or colorectal cancers. If biopsy is required, there will be a minimum of 2-week period after biopsy and before the ablation.
 - HCC patients must meet the United Network for Organ Sharing and Organ Procurement and Transplantation Network (UNOS-OPTN) class 5 criteria for HCC
 - Liver metastases patients must meet minimum criteria of liver biopsy and/or tissue diagnosis of primary tumor or metastatic tumor with new or growing liver tumors radiologically consistent with metastases.
4. Patients with liver cancer not candidates for surgical resection and/or not suitable for other locoregional treatments or patients who have not responded to or relapsed from conventional therapies.
5. Previous treatment with chemotherapy and/or radiotherapy is permitted provided that these treatments have been discontinued more than 2 weeks before the ablation of the targeted tumor and whenever patients have recovered from any related toxicity.
6. Previous treatment with immunotherapies is permitted provided that these therapies have been discontinued at least 4 weeks before the ablation and whenever patients have recovered from any related toxicity.
7. Previous ablation/surgery on other tumors different from those that will be targeted with the VORTX Rx® is allowed whenever a minimum of 2 weeks has elapsed since the prior procedure(s).
8. Tumor(s) to be targeted for ablation will be clearly separated from other tumors or other critical areas upon investigator's criteria.
9. Largest diameter of targeted tumor(s) ≤ 3 cm.
10. Tumor(s) that will be targeted at a depth < 10 cm from the skin surface.
11. Must have an adequate acoustic window in the abdominal space to be able to visualize targeted tumor(s) using ultrasound imaging; also, must be able to visualize targeted tumor using MRI with optional CT imaging at investigator discretion.
12. Patients who can safely undergo general anaesthesia.

13. Liver function score of Child-Pugh A or Child-Pugh B.
14. ECOG PS 0, 1 or 2 at screening.
15. Adequate liver function (ALT and AST < 2.5 x upper limit of normal [ULN]), renal function (serum creatinine <2 ULN and/or bilirubin <2.5 UNL) and hematologic function (neutrophil count > 1.0 x 10⁹/L and platelet > 50 x 10⁹/L).
16. An INR <2 within the last 7 days prior to the ablation in patients receiving anticoagulants, and an INR <1.5 for patients not treated with anticoagulants.
17. Platelets level >50 x 10⁹/L within the last 7 days prior to the ablation

Exclusion criteria

1. Patients who decline or are unable to understand, provide or are unwilling to sign an informed consent form.
2. Pregnant or nursing (lactating) women; women of childbearing potential and sexually active that are unwilling to use adequate contraception (such as oral contraceptives, intrauterine contraceptive device or barrier method with spermicide or surgical sterilization).
3. Targeted tumor(s) not clearly separated.
4. Targeted tumor(s) >3 cm.
5. Tumor that will be targeted >10 cm from the skin surface.
6. Tumor not clearly visible with diagnostic ultrasound and MRI.
7. Liver function score of Child-Pugh C.
8. Liver volume reserve <40% as measured by CT Scan.
9. Major surgical procedure, biopsy or significant traumatic injury <2 weeks prior to the procedure or has not recovered from side effects/complications of such procedure or trauma.
10. Patient who has not recovered to grade 1 or better from any AEs (except alopecia, fatigue, nausea, vomiting) related to previous anti neoplastic therapies.
11. BMI >30.
12. Parkinson's disease.
13. History of bleeding disorders (e.g. von Willebrand disease) or patients suspected to have a bleeding disorder.
14. Not able to temporarily discontinue warfarin, clopidogrel or any other long-acting anticoagulants at least two weeks before the procedure.
15. Initiation of any anticancer treatment during the screening period.
16. Life expectancy to be less than 6 months.
17. ASA score ≥ 4.

18. Unable or unwilling to complete all required screening and/or follow-up assessments.
19. Patients under ongoing treatment with an investigational medication or medical device that conflicts with the study device.
20. Patients for whom the investigator considers that the ablation is not in the patient's best interest.
21. Patients with active alcohol or drug addiction or any other condition that, in the investigator's opinion, would interfere with their ability to comply with the study requirements.
22. Patients with any concurrent condition that, in the investigator's opinion, would jeopardize the safety of the patient or compliance with the protocol.
23. Patients with known sensitivity to topically applied iodine.

3.3 Study Design

This is an open-label (no-masking), non-randomized, multi-center study comprised of three (3) independent centers located in the greater metropolitan Barcelona area.

4 METHODOLOGY

Quantitative variables will be described with measures of central tendency and dispersion: mean, median, SD (standard deviation), Q1 (first quartile) and Q3 (third quartile), minimum and maximum).

Qualitative variables will be described using absolute and relative frequencies (N, %). Two percentage columns will be presented, total percentage (total %) and valid percentage (valid %), that is, the percentage over the sum of valid responses plus missing values and the percentage over the total of valid responses. When there will be not missing values both of them will be equal, and then only one will be shown.

In the analysis of parameters evolution (ablation zone, liver function parameters, immunological parameters, quality of life scores, VAS scale score), among visits, general linear models of repeated measures will be used. With this methodology, it is necessary that the values of the variable must be available at all visits for all patients.

Where an inferential analysis is required, parametric tests shall be used for continuous variables (T-test) that follow a normal distribution. For variables that do not follow a normal (or non parametric) distribution, Mann Whitney (for unpaired data) or Wilcoxon (for paired data) hypothesis tests shall be used.

These tests will be used in all bilateral cases and with a level of significance of 0.05. In cases where a p-value less than 0.05 appears, it refers to the existence of statistical significance.

Due to the number of evaluable patient ablations available, any result from an applied statistical test must be interpreted with caution.

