6.13 Quality of life assessment

The score of each dimension of this scale will be calculated according to the established scoring algorithms:

Scoring the EORTC QLQ-C30 version 3.0

	Scale	Number of items	Item range*	Version 3.0 Item numbers	Function scales
Global health status / QoL	QL2	2	6	29, 30	
Global health status/QoL (revised) [†]					
Functional scales					
Physical functioning (revised) [†]	PF2	5	3	1 to 5	F
Role functioning (revised) [†]	RF2	2	3	6, 7	F
Emotional functioning	EF	4	3	21 to 24	F
Cognitive functioning	CF	2	3	20, 25	F
Social functioning	SF	2	3	26, 27	F
Symptom scales / items					
Fatigue	FA	3	3	10, 12, 18	
Nausea and vomiting	NV	2	3	14, 15	
Pain	PA	2	3	9, 19	
Dyspnoea	DY	1	3	8	
Insomnia	SL	1	3	11	
Appetite loss	AP	1	3	13	
Constipation	CO	1	3	16	
Diarrhoea	DI	1	3	17	
Financial difficulties	FI	1	3	28	

* *Item range* is the difference between the possible maximum and the minimum response to individual items; most items take values from 1 to 4, giving *range* = 3.

† (revised) scales are those that have been changed since version 1.0, and their short names are indicated in this manual by a suffix “2” – for example, PF2.

For all scales, the *RawScore*, *RS*, is the mean of the component items:

$$RawScore = RS = (I1 + I2 + \dots + In) / n$$

Then for **Functional scales**:

$$\square \quad Score = [1 - ((RS-1)/range)] * 100$$

and for **Symptom scales / items** and **Global health status / QoL**:

$$Score = \{(RS - 1) / range\} * 100$$

Examples:

Emotional functioning:

$$RawScore = (Q_{21} + Q_{22} + Q_{23} + Q_{24}) / 4$$

$$EF\ Score = \{1 - (RawScore - 1) / 3\} \times 100$$

Fatigue:

$$RawScore = (Q_{10} + Q_{12} + Q_{18}) / 3$$

$$FA\ Score = \{(RawScore - 1) / 3\} \times 100$$

Missing items:**• Have at least half of the items from the scale been answered?**

- If Yes, use all the items that were completed, and apply the standard equations given on the previous pages for calculating the scale scores; ignore any items with missing values when making the calculations.
- If No, set scale score to missing.
- For single-item measures, set score to missing.

Descriptive statistics (mean, SD, median, Q₁, Q₃, minimum, maximum) of the following continuous variables will be shown:

- Global health status/QoL (revised)
- Physical functioning (revised)
- Role functioning (revised)
- Emotional functioning
- Cognitive functioning
- Social functioning
- Fatigue
- Nausea and vomiting
- Pain
- Dyspnoea
- Insomnia
- Appetite loss
- Constipation

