14 END OF STUDY/PREMATURE WITHDRAWAL

The categorical variables to be described (n, %) are

- Has the patient completed the study according to protocol? if yes:
 - Reason for premature withdrawal
- If patient's death, a list with reasons and if the adverse event has been related will be provided.

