15.2 Secondary objectives

1. **Assessment of the safety profile of the VORTX Rx®.**

This objective is given the answer with the analyses proposed in sections 6.7.2, 6.7.3, 6.7.4, 6.7.5, 6.8, 8.2, 8.3, 8.4, 9.2, 9.3, 9.4, 9.5, 10.2, 10.3, 10.4, 10.5, 11.2, 11.3, 11.4, 11.5 and 12 of this document.

2. **Assessment of local tumor progression by MRI at 1 week, 1 month and 2 months, post-procedure.**

The following analyses will be carried out to respond to this objective:

The number of patients who have indicated local tumor progression **in at least one visit** (1 week, 1 month, 2 months) for each tumor ablated in ablation 1, ablation 2, and ablation 3 will be provided.

3. **Assessment of the involution of the ablation zone 1 week, 1 month and 2 months post-procedure.**

The following analyses will be carried out separately for each tumor (tumor 1, tumor 2, tumor 3....) to respond to this objective:

- Ablation zone volume at 24 hours post-ablation, 1-week, 1 month and 2 months post-ablation will be compared among visit using a general linear model of repeated measures.

In addition:

- Ablation zone volume at 24 hours post ablation vs ablation zone volume at 1 week will be compared using Paired T-Test or Wilcoxon depending on variable distribution.
- Ablation zone volume at 24 hours post ablation vs ablation zone volume at 1 month will be compared using Paired T-Test or Wilcoxon depending on variable distribution.
- Ablation zone volume at 24 hours post ablation vs ablation zone volume at 2 months will be compared using Paired T-Test or Wilcoxon depending on variable distribution.

4. **Assessment of liver panel.**

The following analyses will be carried out separately for each ablation (ablation 1, ablation 2, ablation 3) to respond to this objective:

- AST at Screening and at 24 hours post-procedure and the follow-up visits performed at 1 week, and 1 and 2 months post-procedure will be compared among visit using a general linear model of repeated measures.
- ALT at Screening and at 24 hours post-procedure and the follow-up visits performed at 1 week, and 1 and 2 months post-procedure will be compared among visit using a general linear model of repeated measures.
- GGT at Screening and at 24 hours post-procedure and the follow-up visits performed at 1 week, and 1 and 2 months post-procedure will be compared among visit using a general linear model of repeated measures.

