- AFP at Screening and at 24 hours post-procedure and the follow-up visits performed at 1 week, and 1 and 2 months post-procedure will be compared among visit using a general linear model of repeated measures.

- CA 15-3 at Screening and at 24 hours post-procedure and the follow-up visits performed at 1 week, and 1 and 2 months post-procedure will be compared among visit using a general linear model of repeated measures.
- CA 19-9 at Screening and at 24 hours post-procedure and the follow-up visits performed at 1 week, and 1 and 2 months post-procedure will be compared among visit using a general linear model of repeated measures.

6. Evaluation of quality of life.

The following analyses will be carried out separately for each ablation (ablation 1, ablation 2, ablation 3) to respond to this objective:

- Global health status/QoL (revised) at Screening and 1 and 2 months post-procedure will be compared among visit using a general linear model of repeated measures.
- Physical functioning (revised) at Screening and 1 and 2 months post-procedure will be compared among visit using a general linear model of repeated measures.
- Role functioning (revised) at Screening and 1 and 2 months post-procedure will be compared among visit using a general linear model of repeated measures.
- Emotional functioning at Screening and 1 and 2 months post-procedure will be compared among visit using a general linear model of repeated measures.
- Cognitive functioning at Screening and 1 and 2 months post-procedure will be compared among visit using a general linear model of repeated measures.
- Social functioning at Screening and 1 and 2 months post-procedure will be compared among visit using a general linear model of repeated measures.
- Fatigue at Screening and 1 and 2 months post-procedure will be compared among visit using a general linear model of repeated measures.
- Nausea and vomiting at Screening and 1 and 2 months post-procedure will be compared among visit using a general linear model of repeated measures.
- Pain at Screening and 1 and 2 months post-procedure will be compared among visit using a general linear model of repeated measures.
- Dyspnoea at Screening and 1 and 2 months post-procedure will be compared among visit using a general linear model of repeated measures.
- Insomnia at Screening and 1 and 2 months post-procedure will be compared among visit using a general linear model of repeated measures.

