- Appetite loss at Screening and 1 and 2 months post-procedure will be compared among visit using a general linear model of repeated measures.

- Constipation at Screening and 1 and 2 months post-procedure will be compared among visit using a general linear model of repeated measures.
- Diarrhoea at Screening and 1 and 2 months post-procedure will be compared among visit using a general linear model of repeated measures.
- Financial difficulties at Screening and 1 and 2 months post-procedure will be compared among visit using a general linear model of repeated measures.

7. **Assessment of pain and analgesic requirements after the ablation procedure.**

The following analyses will be carried out separately for each ablation (ablation 1, ablation 2, ablation 3) to respond to this objective:

- VAS score at screening, at 24 hours post-procedure and the follow-up visits performed at 1 week, will be compared among visit using a general linear model of repeated measures.

In addition, the following categorical variable will be described (n, %) (this analysis will be carried out for the total patients):

- Number of patients with at least one drug due to Post-procedure pain (concomitant medication form).

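### The repeated-measures models for 44 secondary variables require a value at every visit, so one missed visit discards observed data or stops the model

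*SAP*

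**What the plan says.** Section 4 (Methodology) prescribes general linear models of repeated measures for ablation zone, liver, immunological, quality-of-life and VAS variables. It adds that, with this method, "it is necessary that the values of the variable must be available at all visits for all patients".

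Section 15.2 then states, variable by variable, that each "will be compared among visit using a general linear model of repeated measures":

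- Item 3, ablation zone volume: 24 hours, 1 week, 1 month and 2 months. The analysis "will be carried out separately for each tumor".
- Items 4 and 5, liver panel and immunology: screening plus the same four visits, separately for each ablation.
- Item 6, quality of life, for example: "Global health status/QoL (revised) at Screening and 1 and 2 months post-procedure will be compared among visit".
- Item 7, pain: "VAS score at screening, at 24 hours post-procedure and the follow-up visits performed at 1 week, will be compared among visit".

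The SAP expects some values to be missing. The questionnaire scoring in Section 6.13 asks whether at least half of a scale's items were answered, and then: "If No, set scale score to missing". Section 14 tabulates "Reason for premature withdrawal" and lists deaths. Neither is linked to the models, and Section 5 defines no set of complete cases.

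**The concern.** The completeness condition is stated but nothing says what to do when it fails: no exclusion rule, imputation or alternative model. Two readings are open. Under the usual one, an incomplete patient or tumor is left out of that variable's model although the other visits were observed. Under the literal one, with its reference to all patients, a single missing value stops the model. The choice would be made after the data are seen.

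The trial has at most ten patients, and the models run separately by ablation or by tumor, so each discarded record costs noticeable precision. If patients miss visits because they are doing worse, the modelled change also describes mainly those who stayed well.

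**Working it through.** **Number of models (Section 15.2).** Ablation volume 1 + liver panel 8 + immunology 19 + quality-of-life scales 15 + VAS 1 = 44. Of these, 1 + 8 + 19 = 28 use four or five visits, all with four post-procedure visits. The other 15 + 1 = 16 use three visits, two of them post-procedure.

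**Assumption.** The SAP gives no missing rate. I take q = 2%, 5% and 10% per post-procedure visit, independently, with screening complete.

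**Formulas.** With k post-procedure visits, expected complete patients of 10 = 10(1 − q)^k. A value that was observed is discarded if any of the other k − 1 visits is missed, so the share discarded = 1 − (1 − q)^(k−1). The chance that all 10 patients are complete = (1 − q)^(10k).

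| | q = 2% | q = 5% | q = 10% |
|---|---|---|---|
| k = 4: complete of 10 | 9.2 | 8.1 | 6.6 |
| k = 4: observed values discarded | 5.9% | 14.3% | 27.1% |
| k = 4: chance all 10 complete | 45% | 13% | 1.5% |
| k = 2: complete of 10 | 9.6 | 9.0 | 8.1 |
| k = 2: observed values discarded | 2% | 5% | 10% |

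The third row matters only under the literal reading. Ablation or tumor strata may be smaller than 10. With 3 units and k = 4, the chance that fewer than two are complete is 1.7%, 9.0% or 27.3%.

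**Precision, random missingness.** Illustrative values, not from the SAP: random-intercept SD 15, slope SD 8 per month, residual SD 8. The variance of one patient's 2-month change is (8 × 2)² + 2 × 8² = 384, so with 10 complete patients the root mean squared error (RMSE) is √(384/10) = 6.20. With complete cases only, averaging 384/m over the binomial number m of complete patients (m at least 2) gives 6.5, 7.0 and 7.9 at 2%, 5% and 10%. Simulation of the five-visit case with n = 10 gave about 6.5, 6.8–7.0 and 7.8–7.9. A mixed model on all available visits gave 6.2–6.4 throughout, close to the no-missing value. At 5% and 10%, coverage of the 95% interval was 94.9% and 94.4% for complete cases, and 93.6% and 93.5% for a random intercept with visit-specific residual variances. A random intercept with one common residual variance covered only 86.7% and 86.4%.

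**Bias, outcome-related missingness.** Illustration: true 2-month change −10, only the 2-month visit missed, 90% retained. The odds of missing it rise by the stated ratio per 10-point worsening.

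| Estimated 2-month change | Odds ratio 1.65 | Odds ratio 4.5 |
|---|---|---|
| Three visits, complete cases | −8.9 | −7.7 |
| Three visits, unstructured, all data | −9.8 | −9.6 |
| Five visits, complete cases | −9.0 to −9.1 | −7.9 |
| Five visits, random intercept with visit-specific variances, all data | −9.3 to −9.4 | −8.7 |

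In the five-visit models the 1-month bias is removed, but most of the 2-month bias remains.

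**The case against.** The strongest reply is that Section 4 merely describes what this kind of model needs, that leaving out incomplete units is the ordinary reading, and that one sentence saying so would close the gap. That sentence would settle which units enter the model, but it would keep discarding observed values when a method that uses them costs almost nothing.

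Several other points stand:

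- Missingness may be low. Follow-up lasts two months, and the exclusion criteria bar anyone "Unable or unwilling to complete all required screening and/or follow-up assessments" and anyone with a life expectancy under six months. At 2% the loss is small.
- The practical gain can be slight. With three visits and 90% retained, RMSE at odds ratios 1, 1.65 and 4.5 is 6.4, 6.5 and 6.6 for the unstructured model, against 6.6, 6.6 and 6.8 for complete cases. At 71% retained and odds ratio 4.5 the unstructured model is worse, 9.7 against 8.7.
- Section 4 already asks for caution in reading any test result.
- The exact covariance structure, and any minimum stratum size for modelling, are matters of preference.

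A reader might infer that the trial's conclusions are biased, or that a mixed model would make all 44 analyses nearly unbiased. The document supports neither. It gives no missing rate or dropout mechanism, so any bias is conditional on assumptions, and the near-unbiased figures belong to the unstructured three-visit model only.

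**Conclusion.** The point holds as a minor one. The all-visits requirement governs 44 secondary models and has no companion rule for a missed visit. At assumed rates of 2% to 10% per post-procedure visit, the cost in the 28 models with four post-procedure visits runs from under one patient in ten to more than three. The size of any bias cannot be fixed from the SAP.

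Not affected are the primary technical-success analysis (Section 15.1), the per-visit tables (Sections 8 to 11), the adverse-event analyses (Section 12), the pairwise volume tests and progression count (Section 15.2, items 2 and 3), and the analgesic count (item 7). The pairwise tests need only two values each, so ablation volume is less exposed than the other 43 variables.

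The retention figures assume independent missingness. The RMSE and bias figures also rest on the illustrative variances.

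**What to change.** In Sections 4 and 15.2, delete the all-visits requirement and fit a linear mixed model to all available visits: REML, visit as a categorical effect, Kenward-Roger degrees of freedom. State the covariance structure in advance, with a simpler fallback if it does not converge. An unstructured covariance is a reasonable choice for the three-visit models, and a random intercept with visit-specific residual variances for the others. Avoid a random intercept with one common residual variance, given its coverage above. Report the change from screening (from 24 hours for ablation volume) with a 95% confidence interval, and the number of complete and incomplete patients or tumors in each model.

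The cost is SAP wording and a different procedure call; no new data are needed. The drawbacks are possible non-convergence with at most ten patients, last-visit coverage slightly under 95% (about 93–94% under random missingness), and, under heavy outcome-related dropout, a larger last-visit error for the unstructured model. The results remain descriptive.

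### Section 4 of the SAP treats every p<0.05 as statistical significance across 43 to 129 unadjusted repeated-measures models, so about 2 to 6 chance findings would be expected if nothing changed between visits

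*SAP*

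**What the plan says.** Section 4 (Methodology) fixes the level for every inferential test: "These tests will be used in all bilateral cases and with a level of significance of 0.05". It then states how a result is to be read: "In cases where a p-value less than 0.05 appears, it refers to the existence of statistical significance". The next paragraph adds a reservation: "Due to the number of evaluable patient ablations available, any result from an applied statistical test must be interpreted with caution".

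The tests themselves are in section 15.2. Objectives 4 (liver panel), 5 (immunologic), 6 (quality of life) and 7 (pain) each open with the same instruction: "The following analyses will be carried out separately for each ablation (ablation 1, ablation 2, ablation 3) to respond to this objective". Under each, every variable gets its own repeated-measures general linear model across visits. Objective 3 (ablation zone volume) is split by tumour rather than by ablation, with an open-ended list: "The following analyses will be carried out separately for each tumor (tumor 1, tumor 2, tumor 3....) to respond to this objective". It has one repeated-measures model and three paired comparisons against the 24-hour volume.

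Section 3.2 limits the study to ten patients: "This study will include up to ten (10) subjects meeting all the inclusion criteria". Section 15.1 answers the primary objective with a percentage and no hypothesis test. The SAP names no family of tests, no order of testing, no adjusted level and no exploratory status for section 15.2.

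**The concern.** The rule in section 4 attaches the word significance to any single p-value below 0.05, and section 15.2 produces many of them. Someone following the SAP to the letter would flag each one. The report would then call some laboratory, immune-marker or quality-of-life changes statistically significant, without telling the reader how many tests were run to find them.

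What is at stake is how the secondary results may be described. With ten patients at most and no comparator, a few isolated significant markers among dozens could be chance, real change after the procedure, or disease course. The rule as written invites the reader to take them as established.

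**Working it through.** The SAP states no test count and no overall error rate, so there is no figure of its own to reproduce. The count comes from section 15.2.

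**Variables modelled per ablation**
- Liver panel: AST, ALT, GGT, alkaline phosphatase, total bilirubin, albumin, PT, INR = 8.
- Immunologic: seven CD markers, C reactive protein, C3, C4, CH50, IgG, IgM, IgA, interleukin-6, CEA, AFP, CA 15-3, CA 19-9 = 19.
- QLQ-C30 scales = 15.
- VAS = 1.
- Total: 8 + 19 + 15 + 1 = 43.

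**Number of models**
- Only ablation 1 analysable: 43 × 1 = 43.
- All three ablations analysable: 43 × 3 = 129.

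**Expected chance findings.** Assume no variable truly changes between visits and each test has 5% size. Then expected number = 0.05 × number of tests. This does not require the tests to be independent.
- 43 models: 0.05 × 43 = 2.15.
- 129 models: 0.05 × 129 = 6.45.

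**Chance of at least one**, which does assume independence (these variables are unlikely to be independent, so this is only a guide):
- 43 models: 1 − 0.95^43 = 0.890.
- 129 models: 1 − 0.95^129 = 0.999.

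**Volume tests.** Objective 3 adds 1 + 3 = 4 tests per tumour index. They are not counted above. Section 2 describes ablated tissue being resorbed and liver growing back, so no change in volume is not a plausible null.

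**Is 5% the right size per model?** It is an approximation. The SAP states no sphericity correction. A simulation of an uncorrected repeated-measures F test was run with 3 to 10 patients and an assumed first-order autoregressive correlation of 0.5 to 0.8. It rejected a true null in 6.2% to 8.2% of runs with five visits (the schedule of the 27 liver and immunologic variables) and in 5.1% to 5.9% with three visits (the 16 QLQ-C30 and VAS variables). With uncorrelated visits the rate was 4.7% to 5.2%. Under those assumed correlations the expected numbers above are slightly low.

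**The case against.** **The SAP already urges caution.** The sentence after the rule covers every test in the plan: "Due to the number of evaluable patient ablations available, any result from an applied statistical test must be interpreted with caution". This softens the reading, and that much stands. But the reason it gives is small numbers. It does not mention how many tests are run, and it does not withdraw the definition of significance placed just before it.

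**The size is easily overstated.** A reader might count all three ablations, assume three tumour indices, and reach 129 + 12 = 141 tests and 141 × 0.05 = 7.05 false positives from a device that does nothing. The document does not support that reading, for three reasons.
- The tumour list is open-ended, so three is an assumption. With up to ten patients, and with section 4 requiring values at all visits, the strata for ablations 2 and 3 may be very small or empty.
- The tests do not ask whether the device has an effect. They ask whether a value changes between visits in an uncontrolled study, where anaesthesia, co-treatment or disease course could also produce real change.
- Volume change is expected on the SAP's own account, so those tests do not belong in the count. The paired ones also follow up the same volume model.

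**Nothing decisive depends on these tests.** This is correct: all serve secondary objectives, and the primary percentage is untouched. That makes the point a cheap improvement, not a threat to the study's main result.

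**Intervals can be misread in the same way.** Changes from baseline number 27 × 4 + 15 × 2 + 1 × 2 = 140 per ablation, or 420 over three, which is more than the number of models. Readers may treat each interval that excludes zero as a finding. This is a fair warning. The answer is to label the intervals as unadjusted for multiplicity and use them to show size and precision.

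**Formal adjustment would cost sensitivity.** This also stands. In so small a study a strict correction could hide a real change in liver function, so adjustment is not asked for here.

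**Conclusion.** The point holds at a moderate size. Section 4 assigns statistical significance to every p<0.05, and section 15.2 supplies 43 repeated-measures models if only the first ablation can be analysed, and 129 if all three can. Nothing in the SAP marks them as exploratory. About 2 to 6 results would be expected to be called significant by chance.

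That range rests on two assumptions: that no modelled variable truly changes between visits, and that each test has 5% size. If some variables do change, fewer true nulls remain and the chance count falls in proportion. The figures are expectations, so it would be wrong to infer that the report is certain to contain several false findings.

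The SAP states the reading rule itself, so this is not a matter left to the protocol.

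**What to change.** Replace the sentence in section 4 that equates p<0.05 with significance by wording such as:

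> All p-values from the analyses in section 15.2 are two-sided, nominal, unadjusted for multiplicity and exploratory. A value below 0.05 will not be reported as establishing a change. The number of tests actually run will be stated with the results. Each model's p-value will be accompanied by the estimated change from the baseline visit named in section 15.2 (24 hours for ablation zone volume), with a 95% confidence interval labelled as unadjusted for multiplicity.

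The existing caution about the number of ablations can stay, since it makes a separate point.

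One detail to settle at the same time: section 15.2 names screening as the VAS baseline, but section 6 describes no VAS at screening, and the first pain assessment listed is at Visit 1 (section 7.1). The baseline for that change needs to be stated consistently.

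Cost: SAP wording and some additional table columns. No patient, visit or measurement changes. The downside is that no secondary result can be called statistically significant.
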